6.1 Risks

Version number 1.8 and January 23, 2024

The most common risks of the wrist cooling device in this study include a reaction that impairs blood flow to the hand and could make it worse for disorders such as Raynaud's phenomenal which is why people with Raynaud's and similar conditions should not take the part in the study. The participant may also experience the coolness as being uncomfortable.

To minimize the risk of adverse events, we will exclude subjects with any history of cold sensitivity to the wrist or hand. In addition, the participant may find the attachment of the device around the wrist to be uncomfortable. We will exclude subjects with a history of experiencing discomfort when placing anything such as a wristwatch on their wrist.

To mitigate discomfort for the device that when activated results in white plate cooling the skin underneath it to a temperature of 47°F we will instruct the participant to press the square button and the temperature will almost immediately increase to 60°F. If it is still uncomfortable the participant has the option of pressing the button again to further increase the temperature to 77°F. They have the other option to shut it off by holding the button down for 2 seconds. The device can also be removed immediately from the wrist which is attached by a Velcro connection that can be easily opened. To mitigate any discomfort for the device that when activated turns on the cooling fan only they will be instructed to press the square button for 2 seconds which will set off the device or they can immediately remove the device from their wrist.

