7.1 Subject Inclusion Criteria

In order to be eligible to participate in this study, an individual must meet all of the following criteria:

a. Experiencing at least 2 hot flashes per day that are either moderate and/or severe in intensity for at least the past 2 months.

Version number 1.8 and January 23, 2024

- Moderate hot flash: sensation of heat with sweating/dampness but able to continue activity with only brief fanning needed
- Severe hot flash: sensation of intense heat with sweating and causing disruption of current activity
- b. English speaking and English writing ability
- c. Must be 21 years old age or older

7.2 Subject Exclusion Criteria:

An adult who meets any of the following criteria will be excluded from participation in this study:

- 1. Temperature sensitivity due to cooling associated with an autoimmune or vascular disorder, such as Raynaud's phenomena, peripheral arterial disease or for any other reasons.
- 2. Any wrist skin sensitivity that is known to cause discomfort when any type of device such as a wristwatch is placed on the wrist.
- 3. Any lack of sensitivity to coolness on the wrists or hands
- 4. Current use of pharmaceuticals or devices to treat hot flashes.
- 5. Unable to understand and speak English and unable to write English

8 Study Intervention:

The subject will be randomized using the computer-generated randomization chart that will be produced by [name]. [name] will not be involved in any of the studies activities associated with interacting with this subject. The subject will be randomized in this double blinded randomized crossover study to use assigned device the depending upon their randomization during weeks 3 and 4 followed by using the other assigned device during weeks 5 and 6. For example, if the subject was randomized to use the device in box B for weeks 3 and 4 then they will be instructed to use the assigned device that in the box A for weeks 5 and 6 of the study. The wrist cooling device. The randomization chart will be given to [name] whose only activity is to keep the chart until the study is unblinded.

Wrist cooling device with a cooling porcelain plate

- The name of the device is Kulkuf
- Device size is 11.25 inches long and is 2.5 inches in width
- Device model is Kulkuf wrist cooling device. One of the devices when turned on will have the fan
 and wrist cooling porcelain plate activated while the other device that is identical in appearance

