 will have the fan working when turned on and the cooling porcelain plate inactivated.

Version number 1.8 and January 23, 2024

- The device contains a mini heat pump attached to a Velcro open sleeve that can be wrapped around and attached to the wrist (Figure 1).
- The device that when turned on results in the cooling fan and cooling porcelain plate to be activated has 3 settings when the square bottom is depressed. When first depressed the device is immediately turned on and generates a cool temperature of 47°F. When the square bottom is depressed a second time the temperature increases to 60°F. When the square button is pressed a third time the temperature increases 77°F. When the square bottom is held down for two seconds the device will stop operating. The device automatically shuts off after 5 minutes.
- The device that when turned on results in the cooling fan being turned on will have the heat pump deactivated and therefore the white cooling porcelain plate will not cool the skin.
- The device will be used whenever a hot flash occurs during weeks 3, 4, 5 and 6 of the study.
- Dhama USA is the manufacturer of the device.
- The devices will be stored in the locked cabinet in [name] office.
- The devices will be supplied at no cost to the subject.

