Wrist cooling device. On the left panel of figure 1 is the front and back of the device that has the cooling porcelain plate (white square). The device is wrapped around the wrist with the cooling porcelain plate on the inside of the wrist (figure 1 right panel). The device will be provided to the subject with the removal of the A or B label (Figure 2). The cooling devices in both boxes are identical in appearance. The subject will place the device on their wrist using the Velcro attachment. Briefly, when activated by pushing the square button the cooling fan in both devices is activated. One of the devices when activated will also have the cooling porcelain plate almost immediately begin to cool to a temperature of 47°F while the other control device will not activate the cooling porcelain plate. If the cooling temperature is uncomfortable the participant will have an opportunity to press the button again and the temperature will increase to 60°F. If this remains uncomfortable the participant can press the button a third time and the temperature will rise to 77°F. For the device that has the fan turned on only the participant can press the square button for 2 seconds to turn it off if for some reason it becomes uncomfortable. The alternative for both devices if uncomfortable the device can be easily removed from the wrist.

The devices will be supplied by the company at no cost and will be stored in [name] laboratory.

Version number 1.8 and January 23, 2024

Figure 1: Wrist cooling device. On the left is the front of the device and on the right is the back of the device that has the cooling porcelain plate. The device is wrapped around the wrist with the cooling porcelain plate on the inside of the wrist.

Version number 1.8 and January 23, 2024

Figure 2: Boxes labeled A and B will be randomized and after the randomization the A and B labels will be removed on the front of the box. The following language "CAUTION - Investigational Device. Limited by Federal (or United States) law to investigational use" to comply with the abbreviated IDE requirements under §812.5 for labeling a nonsignificant risk device.

9 Recruitment and Retention Procedures:

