• If the potential subject passes the pre-screen and agrees to participate, he/she will be invited to participate in the clinical trial. The subject who meets the inclusion criteria to participate in the study and who wish to be consented virtually the PI will meet with the subject by zoom to follow the consenting procedure as outlined in the protocol. The subject will be provided the consent form by email. The subject will have an opportunity to read it and ask questions of the PI or study personnel. The potential subject will be given up to 30 minutes to decide if they want to participate. The PI will

Version number 1.8 and January 23, 2024

obtain a verbal consent by asking the subject do they agree with the consent form? If they agree, the PI or study personnel will document the subject's consent agreement, and this will be noted in the subject's study file. The date and time will be recorded.

- After obtaining verbal consent, the subject will be randomized as outlined in the approved protocol. The subjects who were consented by zoom and who had provided their verbal consent to the PI or study personal will then receive the devices and diaries by United Parcel Service (UPS), United States Parcel Service (USPS) or by Federal Express (FEDEX) that will have a tracking number and signature request documenting that subject received the devices and diaries.
- The subject will be required to return the devices and diaries to the PI or study personnel by using the UPS, USPS, FEDEX return box that will be given to them. The return box will have an account number to pay for the return of the devices and diaries. The box will also contain a return address and have a tracking number. Once the devices and diaries have been received by either the PI or study personnel, the subject will have the option to be sent the commercially available device.

12 Study Procedures

See the Appendix for the schedule of events.

During the screening process, potential participants will be asked with prescreening questionnaire to determine eligibility. Once they are determined to be eligible, they will be invited to participate in the study.

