This study will take at least 6 weeks and up to 8 weeks. In the first visit in person or virtually this is expected to last up to 1 hour, the participant will be given a consent form and have an opportunity to read it. The study personnel or PI will review the information on the consent form and conduct consent discussion. The subject will have an opportunity to ask questions of the PI or study personnel before signing it in person or providing verbal consent virtually. After signing the consent form or giving verbal consent, it will be signed by the PI or study personnel and printed out and put into their file. A copy of the fully signed consent form for subjects who have been seen personally by the PI or study personal will be provided a copy of the signed consent form either in person or by email. The subjects who were consented verbally will receive by email the consent form signed by PI or study personnel with documentation of the time and date that the verbal consent was obtained. Once consenting is complete, the subjects who are seen in person will be given the diaries and the two devices. Those subjects who have completed the consenting process will receive the diaries and two devices by FEDEX, UPS or USPS. The participant will be shown how to attach the devices to their wrist and then shown how to activate the devices and control the temperature and to shut it off either in person or virtually. Written instructions will also be provided to the participant for their reference (see the attachment).

Version number 1.8 and January 23, 2024

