In summary, there will be a total of two in-person visits for BUSM and local subjects and no in person visit for those are participating virtually 1.) During the first visit the subject will undergo consent process and randomization. Those subjects participating at BUSM or locally will receive the two devices and the diaries. Those subjects participating virtually will receive the two devices and diaries by FEDEX, UPS or USPS. They will be instructed how to use the diaries and the devices at the appropriate time. 2.) During the return visit at the end of the study the subject will be asked questions about the use of devices, and they will return the diaries and the devices either in person or by FEDEX, UPS or USPS. They will have the option to receive the commercially available cooling device as compensation for their participation in this study. There will be 3 telephone or zoom call visits including 1-3 days before the subject is scheduled/expected to use the assigned device during weeks 3 and 4 of the study and then a Zoom call our phone call 1-3 days before the subject is scheduled/expected to use the other device during weeks 5

Version number 1.8 and January 23, 2024

and 6 of the study. There may be multiple follow-ups calls if the subject is unable to start using the device on the indicated day. During week 6 before the end of the study they will get a reminder call to come back to return the diaries and the devices. The subjects in the virtual study will be reminded to send back the diaries and devices.

This is a double blinded crossover study; the devices will be in boxes that will be labeled as A or B. Only one co-investigator ([name]), who will not be communicating with the subjects will possess the information as to which one (A or B) of the labeled boxes that have a wrist cooling device that when turned on activates the fan and cooling porcelain plate or a wrist cooling device that when turned on only activates the fan. We will unblind the labels at the completion of the study for data analysis.

13 Assessment of Safety and Data Safety Monitoring Plan (DSMP)

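### Does the device instruction at the first visit break the blind by having both assigned units run before any on-device rating?

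*Combined protocol and SAP*

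**What the plan says.** Section 12 (Study Procedures) describes the first visit. Once consent is complete, "the subjects who are seen in person will be given the diaries and the two devices". The participant is then "shown how to activate the devices and control the temperature and to shut it off either in person or virtually". The schedule of events in Section 18 likewise places receipt of the two devices, and instruction in their use, at baseline.

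The units differ only in what the plate does. Section 8 says that the fan-only unit "will have the heat pump deactivated and therefore the white cooling porcelain plate will not cool the skin". The cooling unit has three temperature settings. Section 6.1 says of it that, if the plate is uncomfortable, "we will instruct the participant to press the square button and the temperature will almost immediately increase to 60°F". For the fan-only unit, only switching off or removal is described. The two units look identical, and the fan runs in both.

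On blinding, Section 12 states: "Only one co-investigator ([name]), who will not be communicating with the subjects will possess the information" about which box holds which unit. The Figure 2 legend in Section 8 adds that "after the randomization the A and B labels will be removed on the front of the box". Section 8 also gives an example of how the sequence is carried out: "if the subject was randomized to use the device in box B for weeks 3 and 4 then they will be instructed" to use the other box in weeks 5 and 6.

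Section 12 has the participant open one box at the start of week 3, after a call from study personnel. Section 11 has virtual participants receive both units by courier after verbal consent.

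**The concern.** Read literally, Section 12 puts two units in the participant's hands and then has someone show how to activate them and adjust the temperature. If that were done with the assigned units, the difference would be apparent almost at once, because one plate cools and the other does not. The safeguard in Section 12 restricts who holds the A/B key. It does not restrict who may switch on or touch the units.

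Three features make this look serious. The primary outcome (Section 4.2.1) is a severity rating made by the participant, so expectation can influence it. The same study personnel later telephone to say which box to open and explain how severity is recorded, so staff who had learned which unit cools would know that participant's sequence. And a participant randomized to the fan-only unit first would have compared the two side by side before period 1, instead of meeting the cooling unit only in week 5.

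**Working it through.** The plan gives no figure for this point, so the check is mainly a reading of the passages together.

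**1. Does any text say the assigned units are run at baseline?** No. Section 12 says the participant is shown how to activate the devices. It does not say with which unit, or whether power is on. The written instructions it cites are an attachment outside the text reviewed, and they may settle the matter.

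**2. Which way does the surrounding text lean?**

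| Text | Bearing |
|---|---|
| Section 12: one box is opened at the start of week 3, with the device and its instructions inside | Suggests boxes stay closed until then |
| Section 12: one instruction serves in-person and virtual participants | Should be deliverable in the same form to both |
| Section 11: virtual participants get their units by courier after consent | They have no units in hand at the first visit |
| Section 18: instruction is at baseline; the only calls are in weeks 2, 4 and 6 | No separate session after delivery is scheduled |
| Section 12: double blind, key held by one person without subject contact | Running both units before staff would defeat the stated aim |

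If the instruction takes place at the first visit, as the schedule says, virtual participants must receive it without their assigned units. The natural reading is an explanation of the buttons, not a trial run. On that reading the passages do not conflict.

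**3. Who would learn what if the units were run?** The participant would feel the cooling directly. For staff it is an inference: with identical units and a fan running in both, they would have to touch the plate or notice the participant's reaction. Extending one viewing to the sequence of all 30 participants needs three things together: the units are run, the letters mean the same for everyone, and staff can still trace the letter after the labels come off. The text does not establish all three.

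**4. What would avoiding a run at baseline protect?** Less than it seems, for two reasons.
- *Participants.* All are told how to control a temperature. Someone starting on the fan-only unit can notice in week 3 that the plate does not cool; someone starting on the cooling unit feels it at once. Unmasking in use does not depend on the first visit.
- *Staff.* Section 13.2 has adverse effects asked about at every call and invites reports of discomfort from coolness. A report of coolness at the week 4 call suggests the period 1 unit, and hence the period 2 unit.

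**5. Can a size be given?** Only for a different question. In a two-sequence crossover the treatment estimate averages the two sequences' mean within-person differences, so a bias b confined to the fan-first sequence shifts it by b/2. Suppose the whole 15–20% placebo response in Section 15.2 vanished in every fan-first participant. The shift would be 15/2 = 7.5 to 20/2 = 10 points, against the planned 60 − 20 = 40. But that is the cost of complete unmasking of those participants from any cause, including ordinary use, and the placebo figure follows a sentence about the number of hot flashes, not their severity. It does not measure what a baseline run would add. An effect on the false-positive rate would also need a standard deviation, which the plan does not state. Nothing in the documents allows a number for staff blinding.

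**The case for a change.** The best case for acting is that a double-blind protocol should close this route in writing, and that doing so costs almost nothing. Opening a box at week 3 is an instruction on use, not a prohibition on opening it earlier, and the boxes are not said to be sealed. A side-by-side comparison before period 1 tells a fan-first participant more than the mere absence of cooling in week 3. The blinding questionnaire in Section 16 comes at the end of the study, so it cannot separate disclosure at baseline from disclosure during use.

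Much of this stands as description: the visible text is silent on whether the units are powered, and the questionnaire cannot date the unmasking. It does not carry the conclusion. The written prohibition would restate what the double-blind design already requires of staff. The obvious practical remedy, a separate demonstration unit that cools, would give every fan-first participant a reference sensation before week 3, which is close to the comparison it is meant to prevent. A common script avoids that, but it is also how one would expect blinded staff to proceed. Staff do not rate the outcome either, so their knowledge could act only through a few calls.

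**Conclusion.** No change to the plan follows. The gap is real but is one of written detail: Section 12 does not say whether the assigned units are switched on at the first visit. The week 3 box opening, the virtual delivery route and the declared blinding all indicate that they are not. Run that way, the trial loses nothing. If a unit were run, the added bias is unquantified. It would come on top of unmasking that ordinary use and the adverse-effect calls can produce anyway.

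This rests on two assumptions: that staff conduct the first visit in keeping with the double-blind design, and that the written instructions in the attachment do not direct them to run both units. If the attachment did so, the conclusion would have to be reconsidered.

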13.1 Definitions for Safety Assessment

The following definitions will be used in the assessment of safety:

Adverse Event (AE) is any untoward or unfavorable medical occurrence in a human subject, including any abnormal sign (for example, abnormal physical exam or laboratory finding), symptom, or disease, temporally associated with the subject's participation in the research, whether or not considered related to the subject's participation in the research.

Serious Adverse Event (SAE) is any adverse event that

- (1) results in death;
- (2) is life-threatening;
- (3) results in inpatient hospitalization or prolongation of existing hospitalization;
- (4) results in a persistent or significant disability/incapacity;
- (5) results in a congenital anomaly/birth defect; or
- (6) based upon appropriate medical judgment, may jeopardize the subject's health and may require medical or surgical intervention to prevent one of the other outcomes listed in this definition (examples of such events include allergic bronchospasm requiring intensive treatment in the emergency room or at home, blood dyscrasias or convulsions that do not result in inpatient hospitalization, or the development of drug dependency or drug abuse).

Life-threatening means that the event places the subject at immediate risk of death from the event as it occurred.

Version number 1.8 and January 23, 2024

Unanticipated Problem is defined as an event, experience or outcome that meets **all three** of the following criteria:

- is unexpected; AND
- is related or possibly related to participation in the research; AND
- suggests that the research places subjects or others at a greater risk of harm (including physical, psychological, economic, or social harm) than was previously known or recognized.

Possibly related means there is a reasonable possibility that the incident, experience, or outcome may have been caused by the procedures involved in the research

Unexpected means the nature, severity, or frequency of the event is not consistent with either:

- the known or foreseeable risk of adverse events associated with the procedures involved in the
 research that are described in (a) the protocol–related documents, such as the IRB-approved
 research protocol, any applicable investigator brochure, and the current IRB-approved informed
 consent document, and (b) other relevant sources of information, such as product labeling and
 package inserts; or
- the expected natural progression of any underlying disease, disorder, or condition of the subject(s)
 experiencing the adverse event and the subject's predisposing risk factor profile for the adverse
 event.

Unanticipated adverse device effect means any serious adverse effect on health or safety or any lifethreatening problem or death caused by, or associated with, a device, if that effect, problem, or death was not previously identified in nature, severity, or degree of incidence in the investigational plan or application (including a supplementary plan or application), or any other unanticipated serious problem associated with a device that relates to the rights, safety, or welfare of subjects.

